3.4 DIETARY INTAKE

Stable dietary intake should be maintained, including high fiber diet, fiber supplements, vitamins and minerals, probiotics, fish oil, etc. during the study. Patients must have been on a stable dietary regimen for at least 30 days before Visit 1, and are expected to remain on that diet, including all supplements, for the duration of the study.

4. VARIABLES AND METHODS OF ASSESSMENT

4.1 DEMOGRAPHICS AND BASELINE CHARACTERISTICS

4.1.1 Patient Demography

Patient demography consists of:

- Age at screening* (date of birth)
- Race
- Ethnicity
- Sex (Gender)
- Height (m), without shoes
- Weight (kg) and BMI

*If a patient is anticipated to turn 12 between screening and randomization, he/she will be randomized into the adolescent group. See section **9.6** for more information on age changes and informed consent/assent.

4.1.2 Disease and Medical History

A complete medical history, including history of GI diseases, should be recorded for all patients. Source documentation for diagnoses, previous treatments and interventions, where available, should be included in the patient's medical record to facilitate source documentation verification. Confirmation of diagnosis of IBS-C is required as part of evaluation for this study; if not previously documented in the patient's medical history, the diagnosis must be included in the patient's medical record for the purpose of source document verification.

4.1.3 Previous Medications and Diet

At the Screening Visit (Visit 1), the clinical site will ensure the patient is not or has not been on prohibited medications, supplements or investigational agents during the specified time (see **Section 3.3.2**). If the patient has used a prohibited medication within the proscribed time period prior to Visit 1, the site needs to ensure that the required washout period for the medication is completed before commencement of the 2-week baseline diary assessments. Previous medications will be documented as described in **Section 3.3**.

The diet history of each patient will be reviewed at Screening (Visit 1) to determine if the patient has been on a stable diet for the last 30 days, and whether the patient agrees to remain on that diet for the duration of the study.

4.2 EFFICACY VARIABLES

4.2.1 Data Collected via the Electronic Diary

At the Screening Visit (Visit 1), patients will be instructed on the use of the electronic diary and the importance of daily diary reports. Episodic or "real time" reporting should be made after each bowel movement or use of rescue medication during the course of the day. End of Day reporting should be made only once per day (between 7 pm to 11:59 pm each day). **Patients will begin using the electronic diary following training at Visit 1 and will continue using it through the Post-Treatment Period.**

The electronic diary will be activated at the Screening Visit (Visit 1) in order for the patient to become familiar with its daily use to record their BMs, rescue medication intake and IBS-C symptoms. Note that any data entered prior to the beginning of the 2-week baseline diary period will be utilized for assessment of compliance only and will not be saved.

The electronic diary is designed for:

- **Episodic reporting** of each bowel movement (BM) and rescue medication (RM) use in “real-time” as they occur throughout a 24-hour period (Patients/caregivers may report BMs and RM use as often as necessary);
- **End-of-Day daily reporting** of constipation-related symptoms (and BM/RM if not already reported as an ‘episodic report’) and fecal incontinence* at a specific time each evening. Patients who have not completed the prompted evening call will receive an automated reminder each evening.

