Spontaneous bowel movement (SBM)	A bowel movement that occurs in the absence of laxative use within the preceding 24 hours
Complete spontaneous bowel movement (CSBM)	A spontaneous bowel movement with the sense of complete evacuation

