19. Patient reports having more than 1 loose, mushy stool (Diary-recorded stool consistency of 6 on the Bristol Stool Form Scale (BSFS or 4 on the modified Bristol Stool Form Scale for Children [mBSFS-C]) or any watery stool (Diary-recorded stool consistency of 7 on the BSFS or 5 on the mBSFS-C) with any SBM that occurred in the absence of laxative use on the calendar day of the BM or the calendar day before the BM during each 7-day (week) period before the randomization day and up to the day of randomization;
20. ≥ 3 CSBMs per week for either week of the 2-week baseline diary assessment immediately preceding the randomization visit;
21. > 6 SBMs per week for either week of the 2-week baseline diary assessment immediately preceding the randomization visit;
22. Patient reports worst abdominal pain intensity (WAPI) scores in the 2-week baseline diary that meet either of the following:
 - a. WAPI score of 0 on the 11-point Numeric Rating Scale or Wong-Baker Faces® Pain Rating Scale for more than two days during each week of the 2-week baseline diary period.
 - b. An average WAPI < 3 for either of the two weeks of the baseline diary;

23. Completion of < 5 of the 7 required daily diary entries in each week of the 2-week baseline diary assessment immediately preceding the randomization visit;
24. Use of rescue medication (Dulcolax®, bisacodyl) for more than 2 days during either of the two weeks of the 2-week baseline diary assessment immediately preceding the randomization visit.

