3.3 PREVIOUS AND CONCOMITANT MEDICATIONS

Any medication the patient takes other than the study drug, including herbal and other non-traditional remedies, is considered a concomitant medication. The following information must be recorded in the eCRF for each concomitant medication: generic name, route of administration, start and stop dates (month and year at minimum), dosage, and indication. Any changes in the dose or regimen of a concomitant medication must also be recorded in the eCRF.

At the Screening visit, patients/caregivers will be asked what medications the patient has taken during the last 30 days. At each subsequent study visit, patients/caregivers will be asked what concomitant medications the patient is currently taking or has taken since their last visit.

Use of rescue medication (Dulcolax®) will be recorded daily in the BM Diary and should not be included under concomitant medications.

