3.3.1 Permitted Concomitant Medications

Rescue Medication (RM) – Dulcolax®

Dulcolax® 5 mg tablets will be dispensed to patients at Visit 1 and resupplied as needed. From Visit 1 and for the duration of the trial, only protocol supplied Dulcolax® is to be used as the “rescue medication” (laxative) - no other laxatives are allowed. The study level allowable dosage for children age 6 to 12 years is one tablet (5 mg daily) and for children 12 years and older the dosage is 1 to 2 tablets daily (5 to 10 mg). Dulcolax® tablets must be swallowed whole.

Patients are instructed to take rescue medication only if it has been at least 72 hours since their last bowel movement. A patient is therefore expected to have no more than two days of RM use in any given week.

Each rescue medication usage will be recorded daily via the electronic diary. Clinical site personnel will review rescue medication use with patients/caregivers during their telephone contact visits and have the option to discontinue participation of patients who do not adhere to rescue medication guidelines.

Patients are advised NOT to take rescue medication for the period from 24 hours before to 72 hours after Day 1 of dosing. This avoids confounding the data collected in the first week of study drug administration and allows for accurate determination of the time to first BM. Dulcolax®. An initial supply of Rescue Medication will be provided to each site from [REDACTED]. For additional bulk supplies of rescue medication, the site will make a request through IWRS. Supplies of Dulcolax® will not be reconciled at the completion of the study. Sites must track inventory of rescue medication supplies as this will not be managed through IWRS.

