***Soiling of underwear in younger children may be indicative of Fecal Incontinence**

To remain eligible for the study, patients must complete at least 5 of the 7 days of electronic End-of-Day diary entries for each of the 2 weeks of Baseline diary period.

Compliance with diary entries should be a focus for patient education at the telephone contact visits and as needed per the judgement of the clinical site staff.

The following endpoints will be assessed using data collected via the electronic diary in “real time”:

• *Frequency of Bowel Movements*

Patients/caregivers will be asked to report each BM experienced.

• *Stool Consistency*

Patients/caregivers will be asked to rate the patient’s stool consistency according to the BSFS (see **Appendix C**) or mBSFS-C (see **Appendix D**), which will be provided to them in the form of a laminated card (and will appear on the appropriate electronic device) at the Screening Visit (Visit 1), and may be referred to as often as necessary throughout the Screening, Treatment and Post-treatment Periods. The BSFS and mBSFS-C are validated measures of stool consistency commonly used in clinical trials.

• *Stool Diameter*

Patients/caregivers will be asked to report the number of large diameter stools. A large diameter stool is defined as one that is large enough to clog the toilet.

• *Use of Rescue Medication (RM)*

Patients/caregivers will report the use of provided rescue medication (Dulcolax®), including time of use and amount of rescue medication used. Use of rescue medication will determine whether a BM was spontaneous, but only this aspect of rescue medication use is part of the primary endpoint.

The following endpoints will be assessed using data collected via the electronic diary at the end of the day:

• *Fecal Incontinence*

As part of the daily diary (end of day), the following question will be asked:

How many episodes of fecal incontinence did you experience today?

0 1 2 3 more than 3

• *IBS Symptoms*

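### Discarding diary entries made before the baseline fortnight leaves some first-day bowel movements without the laxative look-back that defines an SBM

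*Combined protocol and SAP*

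**What the plan says.** The Definition of Terms in the protocol, repeated in SAP 3.3.7, defines an SBM as "A bowel movement that occurs in the absence of laxative use within the preceding 24 hours". Exclusion 19 (Protocol 3.2) uses a wider window for loose or watery stools: it requires "absence of laxative use on the calendar day of the BM or the calendar day before the BM". Protocol 4.2.1 makes the diary the deciding source: "Use of rescue medication will determine whether a BM was spontaneous".

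Rescue bisacodyl is handed out at the screening visit. Protocol 3.3.1 opens its rule with "From Visit 1 and for the duration of the trial, only protocol supplied" tablets, so rescue can be taken in the weeks before the baseline fortnight. Protocol section 1 requires at least one week of diary practice in that time. Section 4.2.1 then says that data entered "prior to the beginning of the 2-week baseline diary period will be utilized for assessment of compliance only and will not be saved".

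Protocol 3.3 says that rescue use "will be recorded daily in the BM Diary and should not be included under concomitant medications", and 3.3.1 says that supplies will not be reconciled. Diary eligibility (Protocol 5.2.2) and the efficacy baseline (Protocol 8.4.3, SAP 3.3.7) both rest on the 14 days before Day 1.

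**The concern.** The classification needs information from one day earlier than the data that are kept. A child may take rescue on the evening of Day -15 and pass a stool on the morning of Day -14. Under the definition that stool is not spontaneous, but the entry showing this lies outside the saved period. Nothing else described fills the gap. Telephone contacts start on Day 3. The Visit 2 check asks which laxative was used, not when. Neither the protocol nor the SAP says how such a stool is to be counted.

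Two uses of the data are exposed. The first is automated eligibility: the IWRS decides, and Protocol 5.2.2 takes evaluation of diary data out of the site's hands, so a misclassified stool is unlikely to be caught. The second is the baseline SBM rate, which is both the reference for the primary endpoint and a covariate in the primary model.

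**Working it through.** **The plan's own figure, for scale only.** The plan gives no figure on this point. Its planning effect is 1.5 SBM/week with SDs 2.3 (placebo, n = 34) and 3.5 (plecanatide, n = 102), from Protocol 8.2.
- SE = √(2.3²/34 + 3.5²/102) = √(0.1556 + 0.1201) = 0.525.
- Power = Φ(1.5/0.525 − 1.960) = Φ(0.897) = 81.5%.

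This matches the stated 81.5% at two-sided alpha 0.05, the level given in Protocol 8.4. Nothing below depends on it.

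**1. Look-back against retained data.** Take a bowel movement t hours after midnight on Day -14. The 24-hour definition needs laxative use from hour t on Day -15. Saved data cover the last t hours, so 24 − t hours are unseen: 16 hours for a stool at 08:00, 4 hours for one at 20:00. If rescue was recorded earlier on Day -14, the stool is already non-spontaneous and the gap does not matter. For exclusion 19, the whole of Day -15 is needed and unseen, whatever the hour.

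**2. Share of days.** 1/14 = 7.1% of the baseline; 1/7 = 14.3% of the first baseline week.

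**3. Effect on one patient's baseline.** Baseline = (week 1 count + week 2 count)/2. One stool wrongly counted as an SBM adds 1/2 = 0.5 SBM/week. Under the opposite default, one true SBM wrongly dropped subtracts 0.5.

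**4. Effect on eligibility, if the unknown is treated as spontaneous.**
- Item 21 (more than 6 SBMs in a week): a true first-week count of 6 becomes 7 and excludes.
- Item 20 (3 or more CSBMs): a true count of 2 becomes 3 if the stool was complete.
- Item 19: one laxative-induced watery stool is enough to exclude.

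**5. Group mean, under stated assumptions.** The documents give no rescue-use rate. Let p be the chance of rescue on Day -15 and m the number of affected stools on Day -14. Mean shift = p × m/2.
- Low: p = 5%, m = 1: 0.05 × 1/2 = 0.025 SBM/week; 0.05 × 210 = about 10 patients.
- High: p = 2/7 (the two rescue days per week that Protocol 3.3.1 expects as a maximum), m = 2: 0.286 × 2/2 = 0.286 SBM/week; 2/7 × 210 = 60 patients.

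Against the planning SDs, this runs from 0.025/3.5 = 0.7% to 0.286/2.3 = 12.4% of an SD. The high end is generous: it uses the expected ceiling for rescue and places every affected stool on Day -14. No comparable range is offered for wrong screen failures, because the documents have nothing to anchor the share of watery stools after rescue.

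**6. Effect on the comparison.** The error is fixed before randomization, so within each age group its expected value is the same in every arm. The expected difference between arms is therefore zero.

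**The case against.** The strongest reply is practical. The baseline window is counted back from Day 1, and the interval between Visits 1 and 2 is flexible (Protocol section 1 and 3.3.2), so which date becomes Day -15 is known only when Visit 2 takes place. A system that picks out the last 14 days at that moment must have held earlier entries. On this view, not saving them means only that they do not become study data. That is plausible, but it is an inference. The wording of 4.2.1 points the other way, and no section tells the IWRS or the SAP programmer to use an earlier entry. Likewise, a diary question on recent laxative use at each stool would close the gap. The diary scripts cannot be read in the public copy and their final text is deferred to the design specifications, so this cannot be excluded. Section 4.2.1 nonetheless makes recorded rescue use decisive.

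Several stronger readings are tempting and do not hold:
- *All first-day stools are unclassifiable.* Only those whose unresolved look-back reaches Day -15 are.
- *The stool is counted as an SBM.* That is a likely default, but no document states it.
- *The treatment period is immune.* Missed diary days are expected there too (Protocol 8.4.1), and the per-protocol set accepts 70% diary compliance (SAP 4.2). Within baseline, 5 of 7 end-of-day entries suffice each week, so up to 2 × 2 = 4 of 14 may be missing.
- *A 0.5 SBM/week shift is a third of the 1.5 planning effect.* The arithmetic is right, but it sets one patient's baseline against a difference between groups.

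It also stands that rescue is meant to follow at least 72 hours without a bowel movement. A child who took it on Day -15 is therefore unlikely to sit at exactly 6 SBMs the next week. The watery-stool route is not weakened in this way, although a failed child may be re-screened with Medical Monitor approval.

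**Conclusion.** The gap is real on the text but small, and of low severity. Some stools on 1 of 14 baseline days cannot be classified by the plan's own definition, and no default is given. Each one wrongly treated as spontaneous moves that patient's baseline by 0.5 SBM/week and may count toward exclusions 19 to 21. The total size is unknown; 0.025 to 0.286 SBM/week in the mean baseline illustrates assumed rescue rates and is not an estimate. A reader might infer that the primary comparison is biased. It is not: the error precedes randomization, is equal across arms in expectation, and baseline is in the model. What remains is slightly noisier baseline adjustment, a possible common shift in the within-arm changes, and possibly some children screened out wrongly.

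**What to change.** Amend Protocol 4.2.1 so that rescue-medication entries, with date and time, are retained for at least the calendar day before the baseline window. Use them only to classify first-day bowel movements, in the IWRS eligibility programme and in the SAP 3.3.7 baseline. All other practice-period data can still be discarded. Add one sentence giving the default when that entry is itself missing.

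Days whose look-back falls outside the retained period then drop from 1 of 14 to 0. The cost is a small edit to the diary and IWRS specification and a line in the SAP. Patients already make the entry, so their burden does not rise, and sample size and power are unchanged. Look-back lost through missed diary days during baseline or treatment is a separate issue that this change does not address.

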***Soiling of underwear in younger children may be indicative of Fecal Incontinence**

To remain eligible for the study, patients must complete at least 5 of the 7 days of electronic End-of-Day diary entries for each of the 2 weeks of Baseline diary period.

Compliance with diary entries should be a focus for patient education at the telephone contact visits and as needed per the judgement of the clinical site staff.

The following endpoints will be assessed using data collected via the electronic diary in “real time”:

• *Frequency of Bowel Movements*

Patients/caregivers will be asked to report each BM experienced.

• *Stool Consistency*

Patients/caregivers will be asked to rate the patient’s stool consistency according to the BSFS (see **Appendix C**) or mBSFS-C (see **Appendix D**), which will be provided to them in the form of a laminated card (and will appear on the appropriate electronic device) at the Screening Visit (Visit 1), and may be referred to as often as necessary throughout the Screening, Treatment and Post-treatment Periods. The BSFS and mBSFS-C are validated measures of stool consistency commonly used in clinical trials.

• *Stool Diameter*

Patients/caregivers will be asked to report the number of large diameter stools. A large diameter stool is defined as one that is large enough to clog the toilet.

• *Use of Rescue Medication (RM)*

Patients/caregivers will report the use of provided rescue medication (Dulcolax®), including time of use and amount of rescue medication used. Use of rescue medication will determine whether a BM was spontaneous, but only this aspect of rescue medication use is part of the primary endpoint.

The following endpoints will be assessed using data collected via the electronic diary at the end of the day:

• *Fecal Incontinence*

As part of the daily diary (end of day), the following question will be asked:

How many episodes of fecal incontinence did you experience today?

0 1 2 3 more than 3

• *IBS Symptoms*

Patients/caregivers will record the frequency and severity of several IBS-related gastrointestinal symptoms in the electronic diary. These symptoms include abdominal pain, abdominal discomfort, and defecation pain. Each will be rated daily on an 11-point Numeric Pain Rating Scale from 0 (NO) to 10 (WORST POSSIBLE) for adolescents (age 12 to <18) (see **Appendix E**) or the Wong-Baker FACES® Pain Rating Scale for children (age 6 to 11) (see **Appendix F**). The exact descriptors for each symptom rating will be appropriate for each symptom (e.g. for abdominal pain and defecation pain 0 = no pain, 10 = worst possible pain).

- *Patient Global Questionnaires*

In addition to the daily BM and gastrointestinal symptom entries via the e-diary, the following patient questionnaires will also be administered during the study visits (prior to any laboratory blood draws):

- Global IBS-Disease Severity,
- KINDL® Health-Related Quality of Life
- Global Relief of IBS Symptoms
- Global Relief of Abdominal Pain
- Treatment Continuation Assessment
- Treatment Satisfaction Assessment

4.3 SAFETY VARIABLES

4.3.1 Collection of Adverse Events

It is the responsibility of the Investigator to ensure that all AEs are collected. This includes both serious and non-serious AEs derived by spontaneous, unsolicited reports of patients, by observation, and by routine open questionings e.g., “How have you felt since I last saw you?”

NOTE: See section 7.1 for additional details on the recording of specific gastrointestinal symptoms related to IBS-C.

For Definitions, Assessments of AEs, Causality, Severity, Recording and Reporting of Adverse Events and Follow Up, see **Section 7**.

4.3.2 Laboratory Variables

Laboratory assessments will be performed by a central laboratory, as identified in the List of Study Personnel. Please see the Laboratory Manual for detailed instructions regarding the collection, processing, and handling of laboratory samples.

The laboratory variables presented in **Table 1** will be assessed in accordance with the Schedule of Assessments (**Table 2**). Routine laboratory tests (serum chemistry [including electrolytes], hematology, and urinalysis) will be performed at Visit 1 (Screening), Visit 2, and Visit 3 (EOT). A 6- to 12-hour fast is suggested for Visit 1 and is highly recommended prior to all visits when blood sampling is scheduled. The timing of other safety tests (e.g., pregnancy tests and drug screen) is presented in the Schedule of Assessments (**Table 2**).

Table 1 **Laboratory Assessments**

Pregnancy test:	Urine pregnancy tests via dip sticks (performed on-site) at all visits with a scheduled pregnancy test
Hematology:	Erythrocytes, mean corpuscular volume (MCV), mean corpuscular hemoglobin (MCH), neutrophils, eosinophils, basophils, lymphocytes, monocytes, platelets, leukocytes, hemoglobin, and hematocrit
Urinalysis:	Specific gravity, pH, protein, glucose, ketones, blood, and microscopic examination of sediment

Table 1 **Laboratory Assessments**

Serum chemistry:	Alanine aminotransferase, aspartate aminotransferase, creatinine, alkaline phosphatase, total bilirubin, direct bilirubin, blood urea nitrogen, total protein, albumin, uric acid, glucose, and cholesterol.
Hormone:	TSH at screening to determine eligibility (T3 and free T4 if TSH is out of range)
Electrolytes:	Sodium, potassium, chloride, magnesium, phosphorus, calcium
PK:	Plecanatide (and SP-338) plasma assessment
Urine screen for select opioids:	Performed in the clinic for methadone, morphine, and oxycodone.

At Screening, any laboratory abnormality considered clinically significant by the Investigator or the Medical Monitor will render the patient ineligible for study enrollment.

Approximately 5.0 mL of blood will be drawn for each hematology sample and approximately 5.0 mL of blood will be drawn for each serum chemistry sample. The volume of blood that will be required for these laboratory tests during the duration of the study, not including possible repeat tests, will be approximately 30 mL.

